## **ECG**

Summary statistics will be presented for ECG variables by visit and treatment group.

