### **2.2 Secondary objectives**

- To demonstrate superiority of secukinumab (low and high dose) in subjects with severe chronic plaque psoriasis with respect to PASI 90 response at Week 12, compared to placebo.
- To assess efficacy of secukinumab in subjects with severe chronic plaques psoriasis with respect to PASI 50 and PASI 100 at Week 12, compared to placebo.
- To assess efficacy of secukinumab in subjects with severe chronic plaque psoriasis with respect to PASI 50, PASI 75, PASI 90 , PASI 100 and IGA mod 2011 0 or 1 at Week 16 and over time up to Week 52.
- To assess the efficacy of secukinumab with respect to changes in PASI score and IGA mod 2011 score at Week 12, compared to placebo, and over time up to Week 52.
- To investigate the effects of treatment with secukinumab with respect to changes in CDLQI at Week 12, compared to placebo, and over time up to Week 52.
- To investigate the effects of treatment of secukinumab with respect to CDLQI 0 or 1 achievement at Week 12, compared to placebo, and over time up to Week 52.
- To evaluate the effects of treatment of secukinumab on disability at Week 12 and over time up to Week 52 by use of the Childhood Health Assessment Questionnaire (CHAQ®), for subjects with history of psoriatic arthritis.
- To investigate the clinical safety and tolerability of secukinumab as assessed by growth, weight gain, tolerability of s.c. injections, vital signs, clinical laboratory variables, ECGs, and adverse events monitoring, compared to placebo.

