**Table 2-3 Rules for selecting values for analysis**

| Timing of measurement  | Type of data                                    | Rule  |
|------------------------|---|---|
| Baseline               | All data  | See Section 2.1.1.3   |
| Post-baseline efficacy | All data except CDLQI, CHAQ                     | 
The measurement closest to the target day will be used. In the event two measurements are taken equally apart (e.g., 1 day before target date and 1 day after), then the earlier one will be used.
 
If two measurements are taken on the same day, then the first one using eCRF visit number.
 
If two measurements have been taken on the same day and same visit, then the worst measurement will be used.
   |
| Post-baseline efficacy | CDLQI, CHAQ                                     | 
The measurement closest to the target day will be used. In the event two measurements are taken equally apart then the earlier one will be used. If two measurements are taken on the same day, the worst measurement will be used.
 
If two measurements have the same value, select then the first one using eCRF visit number.
   |
| Post-baseline safety   | Summary visit information (e.g. lab, ECG, etc.) | 
The (non-missing) measurement closest to the target day will be used.
 
In the event two measurements are taken equally apart (e.g. 1 day before target date and 1 day after), the first one will be used.
 
If two measurements are taken on the same day, then the first one will be used (using the time).
 
If two measurements are taken on the same date/time, then the first visit number will be used (assuming this is the planned visit).
 
If two measurements are taken on the same date/time/eCRF visit number, then the average value of these two results will be used.
 |

|                      |  |   |
|----------------------|--|---|
| Post-baseline safety | Notable abnormalities (e.g. vital signs) and CTCAE grading for laboratory values | The most extreme measurement in the window will be used. Note this means a subject can have a notably high and notably low measurement within a window. |
|----------------------|--|---|

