## **2.9.4 Other safety data**

### **2.9.4.1 ECG and cardiac imaging data**

The following quantitative variables may be summarized if requested: ventricular rate, RR interval, PR interval, QRS duration, QT interval, and corrected QT interval (QTc). Both Bazett (QTcB) and Fridericia (QTcF) corrections will be presented for QTc.

Notably abnormal ECG parameters post-baseline will be summarized by computing the number and percentage of subjects with:

- QTcF > 500 msec
- QTcF > 480 msec
- QTcF > 450 msec
- QTcF changes from baseline > 30 msec
- QTcF changes from baseline > 60 msec
- PR > 250 msec

A by-subject listing of all quantitative ECG parameters will be provided.

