## 4 Change to protocol specified analyses

Following are the changes to protocol specific analysis:

Protocol amendment 3 included the plan for an additional Interim Analysis prior to the Week 24 PEA analysis, once sufficient safety [REDACTED] data had been collected. This analysis aligned with the efficacy extrapolation principle, was expected to provide the basis for a submission package to health authorities (HA), with the intent to allow earlier availability of secukinumab to pediatric patients in countries which accept a submission of clinical data with use of extrapolation methodology. However, due to the acceleration of patient recruitment in the months following the amendment, Novartis concluded that this analysis would no longer bring a considerable time gain for earlier submission. Thus this additional analysis was not performed and the submission of pediatric data will occur according to the initial plan based on the Week 24 PEA.

The following analyses have been removed from the analysis plan:

- The maximum change (maximum decrease and maximum increase) from baseline within treatment period for each laboratory parameter
- The stratified Van- Elteren testing and Hodges-Lehmann estimates for the absolute value and the percentage change from baseline of CDLQI total score.
- “Pure non-responder” imputation will be used, instead of “Modified non-responder” imputation for missing data, as a sensitivity analysis in efficacy analyses.

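### The SAP makes the protocol's by-visit, by-arm ECG summaries optional and does not declare the change

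*Protocol*

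**What the plan says.** The secondary safety objective in Protocol 2.2 is to be assessed by several measures, among them "vital signs, clinical laboratory variables, ECGs, and adverse events monitoring, compared to placebo". SAP 1.2 repeats it.

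For the analysis, the ECG paragraph of Protocol 9.5.3 is one sentence: "Summary statistics will be presented for ECG variables by visit and treatment group". The introduction to Protocol Section 9 defines summary statistics for continuous variables to include the mean, standard deviation and quartiles.

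SAP 2.9.4.1 reads differently: "The following quantitative variables may be summarized if requested: ventricular rate, RR interval, PR interval, QRS duration, QT interval", and then corrected QT by both the Bazett and Fridericia formulas. It does commit to two other outputs:

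- Threshold counts: "Notably abnormal ECG parameters post-baseline will be summarized by computing the number and percentage of subjects with" QTcF above 500, 480 or 450 ms, QTcF change from baseline above 30 or 60 ms, or PR above 250 ms.
- A listing: "A by-subject listing of all quantitative ECG parameters will be provided".

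Elsewhere the SAP treats ECG summaries as planned. Table 2-3 has a value-selection rule for "Summary visit information (e.g. lab, ECG, etc", and Section 2.9 groups ECG with laboratory data and vital signs when it sets the rule for by-period summary tables.

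**The concern.** A table that the protocol promises has become one that may or may not be produced. The SAP does not say who may ask for it, when, or on what grounds. A programmer who follows the ECG section of the SAP could deliver every required output and still give the reader no mean QTcF or PR by arm at any visit, and nothing at arm level for QRS or QT.

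At stake is whether one named component of the paediatric safety objective is reported in the form the protocol set out. Because Section 4 is silent, a reader of the study report would also have no notice that the form had changed.

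**Working it through.** The point rests on comparing texts; the plan gives no figure to reproduce.

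**1. Commitment against option.** The protocol sentence is unconditional and fixes the layout (visit by treatment group). The SAP sentence is conditional and gives no layout. They cover the same data.

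**2. Was the change declared?** SAP Section 4 records that the extrapolation interim analysis was not performed. Under "The following analyses have been removed from the analysis plan" it then gives three items: maximum laboratory change from baseline, the Van Elteren and Hodges-Lehmann analysis of CDLQI, and the switch from modified to pure non-responder imputation. The first is a descriptive safety output of the same kind as the ECG tables, so by the sponsor's own practice a dropped or optional ECG table would belong there. The additional analyses in Section 4.1 do not concern ECG. The SAP document history cites Section 2.9.4 only for vital-sign criteria, and the protocol's amendment summaries mention no change to the ECG analysis.

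**3. Is the SAP consistent with itself?** Table 2-3 and Section 2.9 assume ECG summaries. So do Section 2.1.1.3, with a same-day baseline exception for ECG, and Section 2.1.1.4, which defines on-treatment ECG assessments. These passages say how a summary is built. Section 2.9.4.1 is the one that says whether it is built.

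**4. What is assured for each quantity** if 2.9.4.1 is followed and no request is made:

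| Quantity | Committed arm-level output |
|---|---|
| QTc | Five counts on QTcF; no means |
| PR | One count (above 250 ms); no means |
| QRS, QT | None |
| RR | None |
| Ventricular rate | None from the ECG; mean pulse change by visit and group is mandatory under SAP 2.9.4.2 |

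Of six quantities, two have counts (5 + 1 = 6 criteria) and four have no ECG tabulation. One of those four is covered in substance by pulse.

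**5. Illustration only.** Counts and means carry different information at the planned arm size of 40 (Protocol 9.7).

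- With no child of 40 over a limit, the exact two-sided 95% upper bound is 1 − 0.025^(1/40) = 8.8%.
- For assumed true rates of 1%, 2% or 5%, the chance of seeing none in an arm is 0.99^40 = 67%, 0.98^40 = 45% or 0.95^40 = 13%.
- A difference in mean change between two arms of 40 has a 95% half-width of 1.96 × SD × √(2/40), which is 4.4, 6.6 or 8.8 ms for an assumed SD of 10, 15 or 20 ms.

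The documents give neither outlier rates nor SDs. A percentage bound and a half-width in ms are on different scales and cannot be ranked against each other. They show only that the counts do not stand in for the means.

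**The case against.** The best defence is that nothing has been removed. SAP Section 1 says that the analysis follows Section 9 of the protocol, ECG is absent from the list of removed analyses, and other parts of the SAP provide for ECG summaries. On that reading the protocol sentence still governs and 2.9.4.1 is loosely worded. This stands in part: the documents show an ambiguous SAP and not a clean deletion. It does not settle the matter, since the section that specifies the ECG output is the one that makes it optional.

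Four stronger readings are tempting, and the documents do not support them.

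- *Only rare outliers would be counted.* No outlier rate is given, and the criteria include QTcF above 450 ms and changes above 30 and 60 ms, which need not be rare. SAP Table 2-11 reports ECG notables for induction, where placebo is a reported group, so some comparison with placebo is kept.
- *A shift in heart rate would go unseen.* SAP 2.9.4.2 requires mean change in vital signs, which include pulse, by visit and treatment group. That also bears on RR, which is the inverse of rate.
- *The tables would be requested only after data are seen.* The SAP does not say when a request would be made.
- *A secukinumab-minus-placebo difference with a confidence interval is missing.* Protocol 9.5.3 promises only summary statistics, and neither document plans such contrasts for vital signs or laboratory means. The induction ECG schedule is also not visible in the available text of Protocol Table 6-1, so the visit for such a contrast cannot be identified.

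It is also fair to note that Protocol 3.6 names no QT or conduction risk, that ECGs are read centrally, and that clinically relevant abnormalities after screening are recorded as adverse events (Protocol 6.5.6). These limit the consequence but do not remove the mismatch.

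**Conclusion.** The point holds as a discrepancy between protocol and SAP, and within the SAP. A protocol-specified summary became optional without being declared. If 2.9.4.1 is followed literally, mean QTcF and PR by visit and arm, and any arm-level summary of QRS, RR or QT, may not be produced.

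It is a minor point. The output is descriptive, and the primary analysis, type I error and power do not depend on it. The conclusion rests on the wording alone and needs none of the assumed rates or SDs. It does not show that the ECG tables were dropped, that the choice was driven by data, or that an ECG signal would be missed.

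**What to change.** In SAP 2.9.4.1, replace the conditional wording so that the listed variables will be summarised by visit and treatment group, for observed value and change from baseline. The layout is the one in Protocol 9.5.3. Reporting both observed values and change follows the general rule for continuous variables in SAP 2.1.

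If the sponsor does mean to leave the tables out, the least that is needed is an entry in SAP Section 4 with the reason, and matching edits to Table 2-3 and Section 2.9.

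The cost is one sentence and one standard set of tables. The ECGs are already centrally read, and the rules for baseline, on-treatment status and selection of values are in SAP 2.1.1.3, 2.1.1.4 and Table 2-3. A between-arm difference in mean change with a 95% confidence interval would be an optional addition and is not part of this correction.

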## **Growth and weight gain**

Growth and weight gain will be summarized descriptively.

### **9.5.4 Resource utilization**

Not Applicable.

### **9.5.5 Health-related Quality of Life**

#### **Children's Dermatology Quality of Life Index (CDLQI)**

The CDLQI measures functional disability of subjects with dermatological disorders that are less than 18 years of age and had been utilized as a relevant clinical measure in atopic dermatitis, as well as other dermatitis clinical trials. The CDLQI is a simple, validated, self-administered 10-item questionnaire. The instrument contains six functional scales (i.e., symptoms and feeling, leisure, school or holidays, personal relationships, sleep and treatment). The questions are based on the preceding week to permit accurate recall. For the CDLQI, each question will be answered on a 4-point Likert scale scored from 0 to 3. Seven scores will be derived from the CDLQI: the total score of each of the six dimensions as well as the total score over all items. The higher the score, the more quality of life is impaired.

For each of the seven scores the percentage change from baseline will be derived. Summary statistics will be provided for absolute values as well as for the percentage change by visit and treatment group in contingency tables. The CDLQI 0 or 1 achievement will be analyzed by visit and treatment group.

#### **Childhood Health Assessment Questionnaire (CHAQ©)**

Changes in health-related quality of life for subjects with history of psoriatic arthritis will be measured using CHAQ©.

Descriptive statistics will be used to summarize patient responses on the CHAQ© Questionnaire by treatment, total score and by domain.

For parent's or patients global assessment of patient's overall well-being and of pain (VAS score) summary statistics for the observed values and the change/percent change from baseline will be provided by visit.

#### **9.5.8 Biomarkers**

Not applicable

#### **9.5.9 PK/PD**

Not applicable

### **9.6 Interim analyses**

An interim analysis will be conducted once at least 80 adolescents complete 24 weeks of treatment. The key efficacy and safety data will be reviewed by the DMC to ensure that no serious efficacy or safety concerns are observed with the study treatments. Enrollment of the pediatric population aged 6 to less than 12 years will begin only when the safety and efficacy evaluation is satisfactory based on the DMC's recommendation.

An additional interim analysis, will be conducted once sufficient safety [REDACTED] data have been collected. This analysis, aligned with the efficacy extrapolation principle, is expected to provide the basis for a submission package to health authorities (HA), with the intent to allow earlier availability of secukinumab to pediatric patients in countries which

accept a submission of clinical data with use of extrapolation methodology. This analysis may be performed before all subjects have reached the primary endpoint. It is expected that data from at least approximately 100 patient years of secukinumab treatment will be included in this analysis.

This interim analysis will consist of a Bayesian full extrapolation approach using adult efficacy data along with available pediatric [REDACTED], safety, and efficacy data to support a submission to Health Authorities for plaque type psoriasis in a pediatric population of ages 6 to 18 years. This analysis will use a Bayesian meta-analytic-prediction (MAP) approach ([Neuenschwander 2010](#)) to demonstrate the consistency of efficacy responses between adults and pediatric population. The MAP approach is based on a Bayesian random-effects meta-analysis and provides a prediction of adult efficacy response rates in a new trial. The prediction will take into account uncertainty due to sample size and due to between-trial heterogeneity.

The observed pediatric response rates at Week 12 for PASI 75, PASI 90 and IGA 0/1 in this study will be checked for consistency with predicted response rates based on Novartis adult studies (CAIN457A2302, CAIN457A2303, CAIN457A2308 and CAIN457A2309) using a predictive check method.

Since the planned hypothesis will not be tested at this interim, the type-I error probability will not be adjusted for this interim and full alpha will be kept for the hypothesis test in the final analysis.

A full analysis of all data collected up to Week 24, including primary endpoint at Week 12 will be performed after all subjects have completed either the Week 24 visit or the premature treatment discontinuation visit (i.e., EOI (Week 12 visit) for subjects discontinuing during induction epoch or EOM (Week 52 visit) for subjects discontinuing during the maintenance epoch visit. Data from subjects who have completed the treatment-free follow-up visits up to this time point (after premature discontinuation from the induction or the maintenance epoch) will also be included in this analysis.

Another full analysis of all data collected up to Week 52, including primary endpoint at Week 12 will be performed after all subjects have completed either the Week 52 visit or the premature treatment discontinuation visit (i.e., EOI (Week 12 visit) for subjects discontinuing during induction epoch or EOM (Week 52 visit) for subjects discontinuing during the maintenance epoch visit. Data from subjects who have completed the treatment-free follow-up visits up to this time point (after premature discontinuation from the induction or the maintenance epoch) will also be included in this analysis.

Efficacy and safety data collected during the extension treatment epoch (until the end of study) may be reported yearly in separate reports.

## **9.7      Sample size calculation**

Approximately 160 pediatric subjects from 6 to less than 18 years of age, with 2 subgroups: 6 to less than 12 years of age, and 12 to less than 18 years of age.

Stratification is planned for age (<12 years,  $\geq$ 12 years) and weight (<25kg, 25-<50kg and  $\geq$ 50kg). It will be targeted to have at least 30 subjects in the <12 years subgroup at a minimum. Enrollment of children aged 6 to less than 12 years will proceed after efficacy and

safety data for approximately 80 (approximately 40 treated with AIN) enrolled adolescents (aged 12 to less than 18 years) treated for 28 weeks have been reviewed and deemed satisfactory by a Data Monitoring Committee.

Since two secukinumab dose regimens will be tested versus placebo with respect to the co-primary endpoints (PASI 75 response and IGA 0 or 1 response at Week 12), the type-I-error will be split to 1.25% one-sided for each comparison. With 40 subjects per group and assuming a response rate of 10% for PASI 75 response and IGA 0 or 1 response in the placebo group, the power to show a response rate of 65% for PASI 75 response and 45% for IGA 0 response in the secukinumab groups based on Fisher's exact test (nQuery Advisor 7.0, two group Fisher's-exact test of equal proportions) is approximately 99% for PASI 75 response and approximately 88% for IGA mod 2011 0 or 1 response. For the secondary endpoint of PASI 90 response at week 12, assuming a response rate of 8% in the placebo group, the power to show a significant difference between a secukinumab dose and placebo, assuming a response rate of 39% in the secukinumab groups based on Fisher's exact test (nQuery Advisor 7.0, two group Fisher's-exact test of equal proportions) is approximately 82% for PASI 90 response. The assumed response rates for secukinumab are based on the confirmatory efficacy in severe patients in the adult phase III program. At Week 12, PASI 75 response rates of 11% and PASI 90 response rates of 7% have been reported in the placebo group in [Paller et al \(2008\)](#) for children and adolescents aged 4-17 years.

## **10 Ethical considerations**

### **10.1 Regulatory and ethical compliance**

This clinical study was designed and shall be implemented and reported in accordance with the ICH Harmonized Tripartite Guidelines for Good Clinical Practice, with applicable local regulations (including European Directive 2001/20/EC, US CFR 21, and Japanese Ministry of Health, Labor, and Welfare), and with the ethical principles laid down in the Declaration of Helsinki.

### **10.2 Informed consent procedures**

Eligible patients may only be included in the study after providing written (witnessed, where required by law or regulation), IRB/IEC-approved informed consent, or, if incapable of doing so, after such consent has been provided by a legally acceptable representative(s) of the patient. In cases where the patient's representative gives consent, the patient should be informed about the study to the extent possible given his/her understanding. If the patient is capable of doing so, he/she should indicate assent by personally signing and dating the written informed consent document or a separate assent form. Informed consent must be obtained before conducting any study-specific procedures (i.e. all of the procedures described in the protocol). The process of obtaining informed consent should be documented in the patient source documents.

Novartis will provide to investigators in a separate document a proposed informed consent form that complies with the ICH GCP guideline and regulatory requirements and is considered appropriate for this study. Any changes to the proposed consent form suggested by the

investigator must be agreed to by Novartis before submission to the IRB/ IEC, and a copy of the approved version must be provided to the Novartis monitor after IRB/IEC approval.

In pediatric patients (< 18 years of age) parental permission and, whenever possible, child assent is needed instead of the procedure for informed consent used for research involving adults. In general, one or both parents or a guardian must be provided with the information ordinarily required for informed consent, so that they may decide whether to allow the child to participate, and children capable of assent must also express their willingness to participate. These forms will be submitted for IRB/IEC/REB approval.

Women of child bearing potential should be informed that taking the study treatment may involve unknown risks to the fetus if pregnancy were to occur during the study and agree that in order to participate in the study they must adhere to the contraception requirement for the duration of the study. If there is any question that the patient will not reliably comply, they should not be entered in the study.

[figure not shown]
In the event that Novartis wants to perform testing on the samples that are not described in this protocol, additional Institutional Review Board and/or Ethics Committee approval will be obtained.

During the COVID-19 pandemic or similar major health care disruption that may challenge the ability to obtain a standard written informed consent due to limitations that prevent an on-site visit, the Investigator may conduct the informed consent discussion remotely (e.g. telephone, videoconference). Guidance issued by local regulatory bodies on this aspect prevails and must be implemented and appropriately documented (e.g. the presence of an impartial witness, sign/dating separate ICFs or assent forms by trial subject/ guardian and person obtaining informed consent, etc).

In case Home Nursing (other than study treatment administration) is implemented during the COVID-19 pandemic or similar major health care disruption, a separate Home Nursing informed consent document must be used in addition to the main ICF.

